Précis: This is a phase 2, single center, two-arm double-masked, randomized investigation and modulation of the μ -opioid mechanisms in TMD (in vivo). We will enroll 60 patients with chronic TMD (30 for the active M1 HD-tDCS group and 30 for the sham group). Each participant will undergo the sequence of events and evaluations laid out in the Schematic of Study Design (pages 14-15), which will take approximately 3 months (up to 10 weeks for healthy volunteers [HV]). In addition, we will recruit 20 (or more) age- and gender-matched HV. We will use the PET/MRI data from up to 10 healthy controls who were recruited and scanned during the NIDCR-NIHR56 DE022637 project, for a total of 30 HV. These 30 healthy control volunteers will be compared to TMD patients at baseline; however, they will not be part of the clinical trial. Completion of full protocol enrollment and participation is expected to take approximately 5 years. Data will be collected on paper or electronic CRFs, on mobile devices, or electronically on local systems (PET, MRI, QST), then transferred via HIPAA-compliant methods by the Michigan Medicine system for analysis by study staff.

Objectives: Primary Objective: The primary effectiveness objective is to investigate whether 10 daily sessions of primary motor cortex (M1) HD-tDCS will result in a significant reduction in clinical pain intensity at rest in chronic TMD subjects 4 weeks after completion of HD-tDCS sessions, as measured by a visual analog scale (VAS) pain score.

The secondary objectives are as follows:

- To investigate whether 10 daily sessions of M1 HD-tDCS will result in significant reductions in clinical pain intensity (at rest) and experimental (sustained masseteric pain stress challenge) measures in chronic TMD subjects at 1 week after completion of HD-tDCS sessions, as measured by VAS pain score assessments, obtained during the baseline PET (#1) session and follow-up PET (#2) session.
- To investigate whether 10 daily sessions of M1 HD-tDCS will result in significant short-term and/or long-term changes

in clinical pain intensity and area measures in chronic TMD subjects treated with HD-tDCS compared to those who receive sham treatment, as measured by GeoPain measures.

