- To investigate whether repetitive active M1 modulation induces increase of μ -opioid receptor (μ OR) non-displaceable binding potential (BP_{ND}) in the thalamus and other pain-related regions in the brains of chronic TMD subjects from the baseline PET (#1) session to the follow-up PET (#2) session, 1 week after completion of HD-tDCS sessions.
- To investigate whether any μ OR BP_{ND} changes from baseline PET (#1) session to follow-up PET (#2) session are associated with changes in mean clinical and experimental pain measures, as measured by VAS pain scores in chronic TMD subjects who receive HD-tDCS treatment compared to those subjects who receive sham treatment.
- To investigate whether chronic TMD is associated with μ OR BP_{ND} changes as compared to healthy subjects during baseline PET (#1) session at rest, and during experimental sustained masseteric pain stress challenge.

Population: 60 men or women aged 18 to 65 with TMD
30 age- and gender-matched healthy subjects, in total:
Twenty (or more) subjects will be recruited from the UMHealthResearch.org database, the TMD and orofacial pain clinics at the University of Michigan (UM), and from other clinics in the region. We will also include the PET/MRI data from up to 10 healthy subjects who were recruited and scanned during the NIDCR-NIHR56 DE022637 project, if they are gender and age-matched.

Phase: II

Number of Sites: 1

Description of Intervention: High-definition transcranial direct current stimulation (HD-tDCS)

Study Duration: 5 years

Subject Approximately 3 months
Participation (up to 10 weeks for healthy volunteers)
Duration:
Estimated Time to Complete 4 years
Enrollment:

Schematic of Study Design (Patients with Chronic TMD):

PreScreening (Up to 8 weeks prior to RND)	Phone Call IRB-Approved Prescreening Checklist/Script	
Screening (Up to 3 weeks prior to RND)	Informed Consent Demographics History and Physical Exam Questionnaires	
PET and MRI #1 (Up to 1 week prior to RND)	QST PET #1 Pre-PET Questionnaires Pregnancy Test and Drug Screen CFN (¹¹ C-carfentanil) Injection [Time 0] Masseteric [HT (Hypertonic) Saline] Injection [45-65 min] Post-PET Questionnaires MRI #1 Screening Form (MRI-specific) MRI Questionnaires	
Randomization		
RND or Enrollment (HD-tDCS Week 1)	TMD Active	TMD Control

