The current study will implement the technique described above from our lab²⁷, but will deliver tDCS over 10 days (Monday through Friday for 2 weeks) instead of 5 days. Although mild adverse effects induced by HD-tDCS have been identified, severe and serious AEs are not expected if procedures are followed to ensure that HD-tDCS is conducted within the recommended safety guidelines.

For more safety information on (HD)-tDCS please see the following links:

tDCS (<http://www.jove.com/details.php?id=2744>)²⁸

and

HD-tDCS (<http://www.jove.com/video/50309/technique-considerations-use-4x1-ring-high-definitiontranscranial>)²⁹.

2.3.2 *Hypertonic Saline Challenge*

To observe or measure the response to pain with the PET scan (described in Section 2.3.3), study participants will be subjected to a pain challenge that elicits the release of endogenous opioids and activates the μ -opioid system. This pain challenge will be conducted only during scheduled PET scan(s).

A hypertonic saline challenge will be used to test the capacity of an individual to mobilize neurotransmitters involved in the response to pain. It is hypothesized that this response may be altered using HD-tDCS treatment. Hypertonic saline (5%; less than 5 mL over 20 minutes) will be infused into the masseter muscle during the PET scan, causing persistent pain that fluctuates in nature. The intensity of the pain will be controlled by the individual's experience such that individuals with chronic TMD pain will experience the same subjective pain intensity as those without TMD. The system is calibrated to induce an average target pain intensity of 4 units on a visual analog scale (VAS; 0= no pain, 10= worst possible pain) over a 20-minute period. Other than the risk of experiencing pain, this procedure carries with it the expected local risks, including those due to piercing of the skin with a needle and injection of saline (Figure 5). In performing approximately 70 of these procedures, our group has noticed redness and soreness at the site as the common AEs associated with the procedure.

The hypertonic saline challenge in the masseter muscle was selected for various reasons, including technical elements related to receptor quantification methods (e.g., sustainability and stability over sufficient time so that receptor quantification can

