be obtained³⁰. In addition, it is a challenge with psychophysical responses that closely mimic those reported by TMD patients³¹, as opposed to briefer challenges (e.g., heat pain, ischemic pain model); making it a perfect challenge to compare neuronal mechanisms of pain regulation in healthy controls and TMD patients. In fact, around half of all TMD cases are classified as masticatory myofascial pain, and the masseter muscle appears to be the best target of choice for pain induction, since it is the main site of clinical TMD pain complain³².

The suggested pain challenge has been extensively employed in our center to elicit the release of endogenous opioids and μ -opioid system activation in previous studies, but never for TMD patients (with the exception of our preliminary data). It is also ecologically consistent with the process under study. Receptor binding measures require the utilization of challenges sufficiently long in duration so that a constant state can be achieved. The subject state does not change substantially during the measurement period, and enough data points are collected to permit quantification. Most pain models do not have those characteristics, because pain declines over time if the stimulus does not adapt to the progressive activation of anti-nociceptive mechanisms.

Pain invariably disappears well within 5-10 min of infusion completion. The total volume of 5% hypertonic saline required to maintain the target pain intensity is also an objective measure of "sustained" pain sensitivity. Of note, momentary ratings of pain intensity still allow for sufficient individual variations in overall assessments of pain sensory and affective qualities (MPQ scale), expectations and effectiveness ratings (0-100 scale) (for placebo/active M1 HD-tDCS evaluation), VAS intensity and unpleasantness, and in emotional responses to the stimulus (PANAS), to allow for the examination of relationships between variable.

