Figure 5: **Diagram of System to Induce and Maintain Pain Intensity.** Block diagram to induce and maintain pain intensity between preset VAS scores by infusion of 5% hypertonic saline into the masseter during the PET session. The main feature of the adaptive control delivery system is a proportional-integrative-derivative (PID) controller. It corrects the difference between actual and estimated pain intensities. The adaptive element includes strategies to bring pain intensity back in case the preset bounds are exceeded and recalculates any previously established PID parameters.

2.3.3 **Positron Emission Tomography (PET)**

Positron emission tomography (PET) scans will be used to analyze potential changes in the tissues and organs of interest occurring as a result of treatment with HD-tDCS, particularly potential changes in the thalamic μ OR availability in the brains of TMD patients during masseteric pain. The μ -opioid system is arguably the main analgesic resource in the brain and target of many exogenous opiates, and currently there is no translational method in animals that could consistently reproduce the complex human TMD experience. However, PET is able to provide crucial information of the central μ -opioid activity in humans during clinical and experimental TMD pain. A radioactive drug (tracer) [^{11}C] carfentanil is used to visualize this activity by binding to μ OR available. Potential PET risks include complications associated with venous cannulation, the administration of study radiopharmaceuticals, and the exposure to low level radiation.

During the PET procedure, an intravenous line will be inserted for injection of the radiotracer and collection of blood. The risks of bruising, bleeding, infection, or soreness associated with intravenous catheter placement are similar to the risks associated with blood draws for routine blood testing. Subjects may also experience dizziness or lightheadedness. Highly trained personnel using standard procedures employed in clinical practice will administer this procedure to minimize the risks. If infection does occur, the subject will be treated with appropriate systemic antibiotic therapy or surgical intervention.

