3.2 Study Outcome Measures

3.2.1 *Primary*

The primary effectiveness endpoint will be as follows:

Change in clinical VAS pain score from baseline (Screening Day) to 4 weeks after completion of HD-tDCS sessions (Follow Up #2).

3.2.2 *Secondary*

The secondary effectiveness endpoints will include the following:

- Change in clinical VAS pain score at rest and during sustained masseteric pain stress challenge from baseline PET (#1) session to follow-up PET (#2) session, 1 week after completion of HD-tDCS sessions.
- Short- and long-term changes in GeoPain measures (pain area, intensity, and their summation) from baseline daily over the treatment period and through follow-up (1, 4, and 8 weeks after completion of HD-tDCS sessions).
- Change in μ OR BP_{ND} levels and clinical VAS pain score from baseline PET (#1) session to follow-up PET (#2) session, 1 week after completion of HD-tDCS sessions.
- Change in μ OR BP_{ND} levels at rest and during experimental sustained masseteric pain stress challenge during PET (#1) in chronic TMD patients as compared to healthy subjects.

3.2.3 *Safety*

All adverse events (AEs) will be solicited via generalized questioning at each study visit, beginning after informed consent.

In addition, questionnaires for PET Screening and HD-tDCS AEs will solicit information about the following symptoms/side effects of specific interest for HD-tDCS: headache, neck pain, scalp pain, scalp burns, tingling, skin redness, sleepiness, trouble concentrating, acute mood changes, and “other (specify).” These AEs were chosen because comprehensive reviews and a consensus article regarded them as common^{34,35}.

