Pain questionnaires will be completed again at 4 weeks (Follow-Up #2) and 8 weeks (Follow-Up #3) after the final treatment day (Study Weeks 6 and 10, respectively).

Table 2

SCHEDULE OF EVENTS – I. Procedures

Procedures	Phone PreScreening	Screening	PET/MRI #1 (Baseline) ^{1,2}	HD-tDCS #1-10 ⁸	PET/MRI #2/ Follow-up #1 ^{1,2}	Follow-up #2	Follow-up #3	Early Termination ³
Visit	P	1	2	3A-J	4	5	6	ET
Study Week	-8	-3	-1	1 – 2	3	6 (1 mth)	10 (2 mths)	N/A
Prescreening Script/Checklist	X ⁵							
Informed Consent		X ⁵						
Adverse Events		X ⁵	X ⁵	X	X	X	X	X
Medical/Dental History and Physical		X ⁵						
Medication History/ Concomitant Medications		X ⁵	X ⁵	X	X	X	X	
Quantitative Sensory Testing (QST)			X ⁵		X			
Eligibility Assessment ⁴		X ⁵						
PET Scan 
 Pregnancy Test (Dip)⁷ Drug Screen⁷ Blood sample for biomarkers Masseteric Pain Challenge (5% hypertonic saline) 			X ⁵		X			
Blood sample for genetic testing			X ⁵					
MRI Scan			X ⁵		X			
RANDOMIZATION				Week 1				
HD-tDCS (M-F for 2 weeks)				X ⁶				

¹ Target dates for PET/MRI are the week prior to Day 1 HD-tDCS session (Baseline) and the week after completion of HD-tDCS sessions (Follow-up); an additional week window is allowed to account for scheduling issues.

² Procedures may require more than one clinic visit.

³ Applicable if subject completes an in-person visit.

⁴ If subject is deemed eligible, schedule subject visits and provide subject with instructions for PET & MRI.

⁵ Healthy Volunteer subjects complete only these procedures indicated.

⁶ Missed days can be doubled in the (M-F) x 2 schedule, with study team approval. See Section 7.

⁷ Completed within 24 hours prior to PET session

⁸ HD-tDCS sessions will be scheduled M-F. See Section 7.2.

Table 2
SCHEDULE OF EVENTS – II. Questionnaires

Questionnaires	Phone PreScreening	Screening	PET/MRI #1 (Baseline) ^{1,2}	HD-tDCS #1-10 ⁸	PET/MRI #2/ Follow Up#1 ^{1,2}	Follow Up #2	Follow Up #3	Early Termination ³
Visit	P	1	2	3A-J	4	5	6	ET
Study Week	-8	-3	-1	1 – 2	3	6 (1 mth)	10 (2 mths)	N/A
Demographics		X ⁷						
Beck Depression Inventory		X ⁷						
DC/TMD Examination Form		X ⁷				X	X	
Expectation of Effect VAS		X						
McGill Pain Questionnaire (MPQ) (Long Form)		X						
MPQ (Short Form) ⁶		X	X	X	X	X	X	
Positive and Negative Affect Schedule (PANAS) ⁶		X ⁷	X ⁷	X	X	X	X	
GeoPain (via mobile device) ⁶		X	X	X	X	X	X	
Visual Analog Scale (VAS) ⁶		X	X	X	X	X	X	
Graded Chronic Pain Scale		X			X	X	X	

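### If challenge VAS is the rating that drives the closed-loop pump, part of any change in sensitivity moves into infused volume, which is not a listed outcome

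*Combined protocol and SAP*

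**What the plan says.** The first bullet of section 3.2.2 joins resting and experimental pain: "Change in clinical VAS pain score at rest and during sustained masseteric pain stress challenge from baseline PET (#1) session" to the second PET session, one week after the last stimulation. The matching objective (Protocol Summary and section 3.1.2) adds only that the change is judged "as measured by VAS pain score assessments, obtained during the baseline PET (#1) session and follow-up PET (#2) session". Hypothesis #2 (section 12.1.2) predicts reductions in both.

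Sections 2.3.2 and 8.1.2 describe the challenge. A computer-controlled syringe pump works "to induce and maintain pain intensity between preset VAS scores by infusion of 5% hypertonic saline into the masseter during the PET session" (caption of Figure 5, repeated for Figure 7). "The main feature of the adaptive control delivery system is a proportional-integrative-derivative (PID) controller". On the level, section 2.3.2 states: "The system is calibrated to induce an average target pain intensity of 4 units on a visual analog scale" running from 0 to 10. Section 8.1.2 gives the same target as 40 on a 0–100 scale, averaged over 20 minutes. Both sections intend patients and controls to feel equal pain.

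Two further statements bear on the point. Section 2.3.2 separates the ratings taken from moment to moment from later overall ones: "momentary ratings of pain intensity still allow for sufficient individual variations in overall assessments of pain sensory and affective qualities (MPQ scale" and further items, which include VAS intensity and unpleasantness. Sections 2.3.2 and 8.1.2 also describe the total saline volume needed to hold the target as an objective gauge of sensitivity to sustained pain. Volume does not appear in the outcomes of section 3.2, in the six hypotheses of section 12.1, or in the analyses of section 12.3.2.

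**The concern.** A feedback controller keeps its output steady by moving its input. Here the output is the pain rating and the input is saline. Read literally, the endpoint is the output. If stimulation makes a patient less sensitive, the pump responds by infusing more, and the rating is pushed back toward target. The treatment effect is then split between VAS and volume, and the plan lists only VAS.

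A small or null difference in challenge VAS could then be reported as no effect on experimental pain while the change sits in the pump record. If volume were brought in only after the data were seen, it would be post hoc. Any correlation under Hypothesis #5 that used the same rating would work with a compressed variable.

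**Working it through.** The plan gives no figure for this endpoint to reproduce. Section 12.2 gives power for the primary objective and a confidence interval for a correlation, and nothing for challenge VAS.

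**1. Which rating could the endpoint be?** The patient schematic gives the order "Masseteric [HT (Hypertonic) Saline] Injection [45-65 min] Post-PET Questionnaires". Section 8.1.2 has a 90-minute scan and says that pain is gone within 5–10 minutes of the end of infusion. Table 2, part II, footnote 6 schedules the VAS before and after PET. If the later VAS follows the scan, it comes 90 − 65 = 25 minutes after infusion stops, whereas challenge pain has gone by 65 + 10 = 75 minutes. A rating of current pain at that time would miss the challenge. The endpoint must therefore be either the momentary rating or a recalled overall rating. Section 3.2.2 names neither.

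**2. Ideal steady state on the momentary reading.** Let VAS = r + s × u, with resting pain r, sensitivity s and infusion rate u. Holding VAS at 40 gives u = (40 − r)/s, so volume is proportional to (40 − r)/s. Take r = 0 and let s fall by 30%:
- VAS with the loop closed: 40 before and 40 after.
- Volume ratio: 1/0.7 = 1.43, a rise of 43%.
- VAS at an unchanged infusion rate: 40 × 0.7 = 28, a fall of 30%.

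**3. A real loop holds the target imperfectly.** This 20-minute illustration uses assumed inputs throughout: 90 s lag, a rating every 15 s, no resting pain, sensitivity down 30%. The two values per cell are for assumed starting sensitivities of 250 and 400 VAS units per mL/min.

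| Assumed controller | Mean VAS before | Change in mean VAS | Change in volume |
|---|---|---|---|
| Tight proportional-integral | 36.7; 37.9 | −3.9%; −2.4% | +37.7%; +39.8% |
| Loose proportional-integral | 27.4; 31.8 | −14.6%; −10.1% | +23.0%; +29.4% |
| Proportional only | 27.9; 31.5 | −11.5%; −8.4% | +26.5%; +30.9% |

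Only the tight loop comes near the stated average of 40. In a separate grid of assumed settings with an integral term, the pump ignored errors inside a tolerance band. With bands of 2.5, 5 and 10 units each side, the median share of the VAS fall that survived was 14%, 37% and 82%. Wide bounds would leave most of the effect in VAS.

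**4. What volume would mean.** By the formula in step 2, volume also responds to resting pain. With sensitivity unchanged, resting VAS falling from 30 to 21 multiplies volume by (40 − 21)/(40 − 30) = 1.9. A fall from 20 to 14 multiplies it by (40 − 14)/(40 − 20) = 1.3.

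**The case against.** The strongest reply is that the concern is doubly conditional. It needs the momentary reading and it needs tight bounds. Section 2.3.2 shows that the authors saw the difference between momentary and overall ratings, Table 2 schedules no rating during the infusion, and an overall rating is only indirectly constrained. The controller figures are not shown, so bounds may be given there. Section 12.3.2.2 stands under planned interim analyses, and section 12.4 leaves the final analysis to a separate SAP whose text is not in the combined document. The list in section 3.2.2 is introduced as what the endpoints will include, so it need not be complete. All of this stands, and it is why the point is conditional and carries no estimated size.

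It does not remove the point. The endpoint says during the challenge, and knowing the distinction is not the same as stating which rating is the endpoint. Section 18 says the SAP and Manual of Procedures are not part of the protocol and can change without amendment, so the definition belongs in section 3.2.2.

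A second reply is that volume is itself impure, as step 4 shows. In simulated trials with assumed inputs (24 per arm) where only resting pain fell, by 30%, volume adjusted for its PET #1 value and PET #1 resting VAS differed significantly in 92–96% of runs. Challenge VAS did so in 76–95%. Neither is specific to sensitivity. This limits volume to a companion role but does not favour VAS alone.

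A reader might infer that the endpoint is fixed at 40 and cannot show an effect, or that the trial loses power. The documents support neither. The rating is unnamed and the bounds are not in the text. In simulations with a 20% fall in sensitivity, power ranged from 0.44 to 0.95 for challenge VAS and from 0.82 to 0.94 for volume, depending on the assumed controller.

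**Conclusion.** The point holds conditionally. On the momentary reading, challenge VAS understates a change in sensitivity, by an amount the documents do not allow anyone to compute. The 43% rise in volume at unchanged VAS is the ideal limit for a 30% fall in sensitivity with no resting pain. It is not a prediction for this trial. On the overall reading the effect is smaller, and what remains is that the rating is not named.

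The scope is the experimental half of one secondary endpoint and any correlation that uses it. The primary endpoint (clinical VAS from Screening to Follow-Up #2), resting VAS, GeoPain and the binding-potential endpoints are untouched. Nor does it follow that the challenge is badly designed: equal pain intensity suits a comparison of opioid activation. The gap lies in what is declared as the outcome, and closing it is a cheap improvement.

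**What to change.** (a) In section 3.2.2 and in the SAP for the final analysis, pre-specify total infused saline volume over the 20-minute challenge as a companion experimental-pain outcome for Hypothesis #2. Compare the arms on PET #2 volume, adjusted for PET #1 volume and PET #1 resting VAS taken before the challenge. Report it beside challenge VAS, with no separate confirmatory claim.

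(b) In section 3.2.2, state whether challenge VAS is the momentary rating or the overall post-challenge rating, and how it is summarised. If it is momentary, state that a null result on it alone will not be read as no effect on experimental pain.

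Cost: a few sentences of wording and retention of the pump log for every session, with no new visit and no change to the challenge. The downside is interpretive. Volume also rises when resting pain falls, which the trial itself hopes to see, so a higher volume alone does not prove lower sensitivity. The SAP should say so.

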2.3 Potential Risks and Benefits

The following potential risks and benefits are applicable to all subjects enrolling in this study, whether patients or healthy volunteers, except those addressing High-Definition Transcranial Direct Current Stimulation (HD-tDCS). Only patients randomized to the clinical trial (treatment or sham arm) will receive this application.

For a schedule of each procedure, see Section 7, Tables 1 & 2 “Schedule of Events” for TMD patients or healthy volunteers.

2.3.1 *High-Definition Transcranial Direct Current Stimulation (HD-tDCS)*

In our study, only TMD patients will receive (HD)-tDCS application. This study will employ a novel, high-definition transcranial direct current stimulation (HD-tDCS) montage created by our group¹⁴ to assess whether tDCS can modulate the μ -opioid dysfunction in TMD patients. Preliminary evidence indicates that HD-tDCS sessions reduced exclusively “contralateral” sensory-discriminative clinical pain measures (intensity/area) in chronic TMD patients by precisely targeting the M1 region¹⁵.

Transcranial DCS has been used increasingly worldwide in recent decades and has been tested and implemented in several research projects in healthy subjects (e.g., cognitive tests, memory) and for the treatment of a variety of conditions from neuropsychiatric illnesses to chronic pain across patients of a wide age range (children, adolescents, adults, and the elderly)^{16,17,18}. Chronic pain conditions that have responded effectively to tDCS include spinal cord injury, fibromyalgia, diabetic polyneuropathy, pelvic pain, multiple sclerosis, and back pain.

Transcranial DCS is a noninvasive technique in which weak, constant, direct current (e.g., 1 to 2 mA) is applied to an area of the brain through electrodes placed on the scalp to modify excitability and reduce pain. Generally, these treatments employ tDCS at low current densities and low maximum total charges with minimal side effects.

In 2011, Brunoni et al.¹⁹ published a systematic review of data from tDCS studies performed up to 2010, which included 172 published articles. Although 63% of the articles reported at least 1 adverse effect (AE), systematic analysis revealed that the rates of most common adverse effects did not differ between the active and sham arms in these studies. Common AEs included itching (39.3% vs. 32.9%, respectively), tingling (22.2% vs. 18.3%), headache (14.8% vs. 16.2%), burning sensation (8.7% vs.

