10%), and discomfort (10.4% vs. 13.4%). Erythema is significantly more common in the active vs. sham group in multiple studies, which is generally benign but could endanger study masking in randomized, sham-controlled trials. On rare occasions, the tDCS application has led to skin burns; however, this side effect appears to occur only when standard procedures for tDCS application are not followed, such as correct preparation of the skin, humidification of sponges with saline, and limiting of voltage/current. No serious adverse events (SAEs) attributable to tDCS have been reported in more than 10,000 subjects investigated in the contemporary tDCS literature from 1998 through 2014. These results suggest that tDCS implemented according to accepted tDCS safety guidelines and procedures is associated with relatively minor AEs.

One crucial consideration for the safety of tDCS is the current density that is being transmitted during treatment. Liebetanz et al.²⁰ reported a study conducted in 58 rats that received single cathodal stimulations at 1-1000 μ A for up to 270 min through an epicranial electrode (3.5 mm²) followed by histological evaluation 48 hours following treatment. A threshold estimate for current density was calculated from volumes of the direct current-induced lesions. No pathological brain lesions were observed below a charge density threshold of 52400 C/m². This threshold was at least 2 orders of magnitude higher than the charge density currently applied in human clinical studies at that time (171–480 C/m²). This study provides a valuable guideline when either raising the current density being used for treatment or looking to alter the method of tDCS delivery.

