Electrical fields generated by conventional tDCS analgesic montages are widely distributed across the brain, lacking specificity on the pain-related structures that are best targeted for the potential relief of TMD pain. High-definition tDCS has been utilized in multiple published studies^{21,22,23,24}. A novel HD-tDCS approach was developed by Villamar et al. (2013) to more precisely target the cortical areas of interest. Our group has further optimized the HD-tDCS montage for noninvasive putative M1 modulation for effective analgesia. A pilot study investigating the effect of 5 daily HD-tDCS sessions on the modulation of pain and motor dysfunction in TMD was published by Donnell et al.²⁵ in 2015. A modified 2x2 HD-tDCS montage was developed and used, with four electrodes arranged at the corners of a 4 cm 4 cm square centered over the caudal portion of the putative M1 (Figure 4), where the homuncular head and facial region is represented. The treatment procedure was identical to that proposed for the study described in this document.

Figure 4: **Brain modulation using 2×2 HD-tDCS Montage.** **A.** 3D rendered head built from the MRI-derived segmentation masks used in the study. Anode electrodes (red) were placed over C4 and C6 and Cathode electrodes were placed over FC4 and FC6. **B.** Skin, skull and CSF masks are suppressed to reveal the underlying gray matter mask. **C.** Induced cortical surface electric-field magnitude plot for 2 mA stimulation. **D.** Induced cortical surface electric-field directional plot for 2 mA stimulation. Red denotes inward (anodal) stimulation while blue denotes outward (cathodal) stimulation.

The previous HD-tDCS study in TMD reported a low rate of mild AEs²⁶. The most commonly reported side effects (occurring at least once per patient during the study) were sleepiness, tingling, headache, scalp pain, a burning scalp sensation, and neck pain. No skin lesions were observed. During any given appointment, patients in the active group experienced an average of 3.33 side effects per session, while patients in the sham group experienced an average of 3.32 side effects per session, out of 10 possible side effects.

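### The tDCS side-effect form has no row for itching, the most frequent event in the protocol's own cited figures, and leaves burning sensation unclear

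*Combined protocol and SAP*

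**What the plan says.** Section 3.2.3 (Safety) sets two routes for collecting adverse events. The first is open: "All adverse events (AEs) will be solicited via generalized questioning at each study visit, beginning after informed consent". The second is a questionnaire that names "headache, neck pain, scalp pain, scalp burns, tingling, skin redness, sleepiness, trouble concentrating, acute mood changes" and ends with an open *Other (specify)* entry. The reason given for the named items is: "These AEs were chosen because comprehensive reviews and a consensus article regarded them as common".

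The tDCS Side Effects form in the appendix has the same nine rows plus *Other*. Each row is graded for severity and for relation to tDCS. Table 2 schedules it at the HD-tDCS sessions, at PET/MRI #2 and at both later follow-ups.

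Section 2.3.1 gives two sets of background figures. From a systematic review of tDCS studies up to 2010, active versus sham: "Common AEs included itching (39.3% vs. 32.9%, respectively), tingling (22.2% vs. 18.3%), headache (14.8% vs. 16.2%), burning sensation (8.7% vs" and, continuing over the page, "10%), and discomfort (10.4% vs. 13.4". From the earlier five-session HD-tDCS study in TMD, the most commonly reported effects were "sleepiness, tingling, headache, scalp pain, a burning scalp sensation, and neck pain", with no skin lesions seen.

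Section 12.3.1 summarises all adverse events by treatment group, severity and relationship. It then tests the safety of HD-tDCS by comparing, between arms, the share of subjects with each solicited event.

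**The concern.** A list justified as the common effects leaves out the event that the protocol's own cited review ranks first. It also has no row that clearly means burning sensation, which both background sources report.

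This matters because a named row is put to every subject at every scheduled visit and graded the same way in both arms. An unnamed symptom is recorded only if the subject volunteers it or writes it in. The two kinds of data do not give comparable proportions, and volunteered reports usually run lower. Since the between-arm comparison in 12.3.1 is defined on solicited events, itching would have no clearly prespecified comparison. Any burning sensation would be split unpredictably between *Scalp Burns*, *Other* and nothing.

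**Working it through.** **Step 1: match the cited rates to the form.** Rates are from section 2.3.1; rows are from section 3.2.3 and the appendix form.

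| Event | Active | Sham | Rank (both arms) | Row on the form |
|---|---|---|---|---|
| Itching | 39.3% | 32.9% | 1 | none |
| Tingling | 22.2% | 18.3% | 2 | yes |
| Headache | 14.8% | 16.2% | 3 | yes |
| Discomfort | 10.4% | 13.4% | 4 | none |
| Burning sensation | 8.7% | 10% | 5 | not by name; nearest is *Scalp Burns* |

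Itching is cited at nearly twice the rate of the next event: 39.3/22.2 = 1.8 in the active arm and 32.9/18.3 = 1.8 in sham.

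**Step 2: match the earlier HD-tDCS study.** Five of its six most common effects are on the form by name. The sixth, burning scalp sensation, is there only if *Scalp Burns* is meant to cover it. Itching is not among the six.

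**Step 3: does *Scalp Burns* mean the sensation?** Section 2.3.1 keeps the two apart. It lists burning sensation among common events, then describes skin burns as rare and tied to departures from standard procedure. For the earlier study it reports a burning sensation as common alongside no skin lesions. Read that way, *Scalp Burns* is the injury. Against that, the row sits on a self-report symptom list graded from absent to severe. The earlier study counted effects "out of 10 possible side effects", and the present form also has ten rows (nine named plus *Other*). The text does not settle it.

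**Step 4: expected numbers.** The plan states no rate, test or power for the safety comparison, so there is no design figure to reproduce. With 30 per arm (section 12.2), and assuming the cited percentages are per-subject risks:

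- Itching: 30 × 0.393 = 11.8 active; 30 × 0.329 = 9.9 sham; about 22 of 60 in all.
- Burning sensation: 30 × 0.087 = 2.6 active; 30 × 0.10 = 3.0 sham.

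**Step 5: what a named itching row could show.** Two-sided alpha of 0.05 is assumed.

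- Difference: 0.393 − 0.329 = 0.064.
- Mean proportion: 0.361. Standard error under the null: √(2 × 0.361 × 0.639 / 30) = 0.1240.
- Standard error under the alternative: √((0.393 × 0.607 + 0.329 × 0.671) / 30) = 0.1237.
- Power ≈ Φ((0.064 − 1.96 × 0.1240) / 0.1237) = Φ(−1.45) ≈ 7%. Fisher's exact test gives 4.6%.
- At 24 per arm the figures are about 7% and 4.2%.
- About 883 per arm would be needed for 80% power.
- The 95% interval for the difference would be about 6.4 ± 24 percentage points (1.96 × 0.1237 = 0.24).

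For burning sensation at 30 per arm, power is about 4% (Fisher 0.9%).

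**The case against.** The case for leaving the form alone has real substance.

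- **The form does cover much of what is common.** Tingling and headache, ranked second and third, are on it. So is skin redness, matching erythema, which section 2.3.1 says is significantly more common under active stimulation. A reader might infer that the safety comparison misses the commonest effects in general. It does not: it misses the first-ranked one and is unclear on the fifth. Discomfort, ranked fourth, is also unnamed.
- **Nothing is lost outright.** Itching can be written under *Other*, which carries the same severity and relatedness columns, or raised at general questioning. It then enters the by-arm summary. This stands: the problem is under-ascertainment, not absence.
- **The rates may not transfer.** They come from tDCS studies in general, whereas this trial uses small gel-filled ring electrodes. The earlier HD-tDCS study in TMD does not report itching among its commonest effects. Section 2.3.1 also does not say whether the percentages are of articles or of subjects. This stands as a caveat on size.
- **The sources differ.** Section 3.2.3 rests its list on other references than the review that gives the itching rate, so this is not a strict contradiction. It is still a mismatch within one protocol, which itself calls itching common.
- **Any gain is descriptive.** The power figures confirm this.
- **Section 12.4 defers the final analysis to a separate Statistical Analysis Plan**, which might define the safety comparison further. It cannot recover an item that the form never asked about.

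The open wording of 3.2.3 does not rescue the plan either. If general questioning makes every event solicited, the phrase in 12.3.1 no longer defines a list of events to compare.

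**Conclusion.** The point holds in a limited form. Itching, first in the protocol's own cited figures, has no named row. Burning sensation is not clearly captured, because *Scalp Burns* can be read as the injury. Under section 12.3.1 as written, itching would have no comparable item-level proportion by arm, though it would still appear in the overall adverse event summary.

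The size is about 12 versus 10 of 30 subjects with itching and about 3 per arm with a burning sensation. This rests on two assumptions: that the cited rates are per subject, and that they carry over to this HD-tDCS montage. The second is uncertain. No efficacy result depends on the point, and no safety test on these items would be powered.

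A reader might also infer that itching and burning are the main cues by which subjects would guess their arm. The documents do not support that. Section 2.3.1 names erythema as the threat to masking, the cited burning rate is slightly higher in sham, and Table 2 schedules a separate sham/placebo assessment.

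This is a low-cost improvement to safety data collection, not a flaw in the trial's main inference.

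**What to change.** 1. Add an *Itching* row to the tDCS Side Effects form.
2. Either add a *Burning sensation* row separate from *Scalp Burns*, or reword that row so that sensation and skin injury are recorded distinctly.
3. Make the same changes to the list in section 3.2.3.
4. State in section 12.3.1 that the comparison covers the named rows of the form, including the new ones, and report these as proportions by arm with intervals rather than as a powered test.

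The cost is one or two extra rows on an existing questionnaire, with no change to visits or treatment. Subjects already treated will lack the items, so the new rows should be reported only for subjects who completed the revised form, with that denominator stated.
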